## 4 OBJECTIVES AND ENDPOINTS

The objectives and endpoints for this study are shown in Table 4-1.

**Table 4-1: Objectives and Endpoints**

Objectives	Endpoints
For Part 1, 2A, 2B Primary 

• To characterize the safety, tolerability, and DLTs and to determine the MTD/RP2D of BMS-986288 administered as monotherapy and in combination with nivolumab in participants with select advanced solid tumors

	

• Incidence of AEs, SAEs, AEs meeting protocol-defined DLT criteria, AEs leading to discontinuation, and death.

For Part 1, 2A, 2B Secondary 

• To characterize the PK of BMS-986288 when administered alone and in combination with nivolumab

• To assess the preliminary efficacy of BMS-986288 alone and in combination with nivolumab in advanced solid tumors using RECIST v1.1

	

• Summary measures of PK parameters of BMS-986288

• ORR, DOR, PFS, and TTR per RECIST v1.1 by Investigator assessment

For Part 1, 2A, 2B Exploratory 

• To explore the potential association between anti-tumor activity and pharmacodynamic markers, such as, but not limited to, [REDACTED] prior to treatment and following administration of BMS-986288 alone and in combination with nivolumab

• To explore the associations between BMS-986288 PK, safety, efficacy, and clinical biomarkers

• To characterize the immunogenicity of BMS-986288 and nivolumab

• To assess the preliminary efficacy of BMS-986288 alone and in combination with nivolumab in select advanced solid tumors using iRECIST

• To assess the OS in participants treated with BMS-986288 alone and in combination with nivolumab

• To assess the potential effect of BMS-986288 when administered [REDACTED] on the QTc interval

• To characterize the PK and bioavailability of BMS-986288 when [REDACTED]

• To explore the impact of treatment on NSCLC participant-reported symptoms and health-related quality of life (Part 2A and Part 2B only)

• To explore participant overall perception of bother in relation to treatment-related symptomatic side effects (Part 2A and Part 2B only)

• To explore overall health status (Part 2A and Part 2B only)

	

• Summary measures of anti-tumor activity by pretreatment level of biomarkers of interest; correlation/measure of association of anti-tumor activity and change (or % change) from baseline in biomarkers of interest

• Association measures between BMS-986288 PK levels by [REDACTED], select outcomes, and biomarkers of interest

• Incidence of ADA to nivolumab and BMS-986288

• ORR, DOR, and PFS per iRECIST by BICR

• OSR at 1 year and 2 years

• Summary measures of ECG parameters and changes in QTcF (<math>\Delta</math>QTcF) from baseline

• Summary of PK parameters when BMS-986288 is [REDACTED] alone or in combination with nivolumab

• Mean NSCLC-SAQ scores and change from baseline scores

• Proportion of participants endorsing each response option of the FACIT GP5

**Table 4-1: Objectives and Endpoints**

Objectives	Endpoints

 
To measure [REDACTED], and assess [REDACTED] change over time and in association with response
 
	
 
Mean EQ-5D-5L utility index scores and EQ-5D-VAS scores and change from baseline scores
 
Summary measures of [REDACTED] and correlation/ measure of association of anti-tumor activity and change (or % change) from baseline in [REDACTED]
 

For Part 2C Primary 
 
To compare the efficacy of BMS-986288 in combination with nivolumab vs regorafenib in the 3L/4L MSS CRC setting.
 
	
 
ORR per RECIST v1.1 by BICR
 

For Part 2C Secondary 
 
To compare the efficacy of BMS-986288 in combination with nivolumab vs regorafenib in the 3L/4L MSS CRC setting
 
To characterize the safety and tolerability of BMS-986288 in combination with nivolumab vs regorafenib in the 3L/4L MSS CRC setting
 
	
 
DOR and PFS per RECIST v1.1 by BICR, and OS
 
ORR, DOR, and PFS per RECIST v1.1 by Investigator assessment
 
Incidence of AEs, SAEs, AEs meeting protocol-defined DLT criteria, AEs leading to discontinuation, and death
 

For Part 2C Exploratory 
 
To compare the efficacy of BMS-986288 in combination with nivolumab vs regorafenib in the 3L/4L MSS CRC setting in subgroups of [REDACTED] and mutant tumors
 
Explore the association between response with both baseline and pharmacodynamic markers in the [REDACTED]
 
To evaluate BMS-986288 PK in the MSS CRC setting in combination with nivolumab
 
To evaluate immunogenicity of BMS-986288 and nivolumab when administered as combination
 
To explore the exposure-response relationship for BMS-986288 when given as combination with nivolumab
 
	
 
ORR, DCR, DOR, PFS by BICR, and OS in the subgroups of [REDACTED] and [REDACTED] participants
 
Summary measures of change (or % change) from baseline in parameters of interest and correlation/measure of association of response and pharmacodynamic markers
 
Summary measures of PK parameters from population PK analysis
 
Summary of ADA incidence and association with PK, efficacy, hypersensitivity, and infusion-related safety events
 
Exposure-response relationship for efficacy endpoints including ORR and PFS.
 
Exposure-response relationship for safety endpoints including TRAE Grade 3+ and dose modification due to TRAE.
 

Abbreviations: 3L/4L = 3rd line/4th line; ADA = anti-drug antibody; AE = adverse event; BICR = blinded independent central review; BMS = Bristol-Myers Squibb; CRC = colorectal cancer; DCR = disease control rate; DOR = duration of response; DLT = dose-limiting toxicity; ECG = electrocardiogram; EQ-5D-5L = 5-Level EQ-5D; EQ-5D-VAS = EQ-5D Visual Analog Scale; FACIT GP5 = Functional Assessment of Chronic Illness Therapy, General Physical item; IgG = immunoglobulin G; iRECIST = modified RECIST in cancer immunotherapy trials; MSS = microsatellite

stable; MTD = maximum tolerated dose; NSCLC-SAQ = Non-small Cell Lung Cancer Symptom Assessment Questionnaire; ORR = objective response rate; OS = overall survival; OSR = overall survival rate; PFS = progression-free survival; PK = pharmacokinetics; QTc = QT interval corrected; QTcF = QT interval corrected for heart rate using Fridericia's formula; RECIST = Response Evaluation Criteria in Solid Tumors; RP2D = recommended Phase 2 dose; SAE = serious adverse event; [REDACTED] TRAE = treatment-related adverse event; [REDACTED] TTR = time to response.

## 5 STUDY DESIGN

### 5.1 Overall Design

This is a Phase 1/2, open-label study of BMS-986288 administered as a single agent and in combination with nivolumab in participants with select advanced solid tumors (SCCHN, NSCLC, cutaneous melanoma, RCC, CRC, TNBC, urothelial carcinoma, gastric, esophageal, and cervical cancer). The study is composed of 2 parts: dose escalation and initial dose expansion.

Part 1: The Dose-Escalation Phase is where the dose of BMS-986288 will be administered IV alone (Part 1A) or in combination with nivolumab (Part 1B). [REDACTED] administration of BMS-986288 as a monotherapy (Arm A) or in combination with nivolumab (Arm B) may also be evaluated [REDACTED].

- The BMS-986288 Monotherapy Escalation (Part 1A) will escalate the dose of BMS-986288 to determine the monotherapy maximum tolerated dose (MTD)/recommended Phase 2 dose (RP2D). Specifically, the Part 1A dose escalation will evaluate different doses of BMS-986288 starting at [REDACTED] mg, followed by [REDACTED]. If it appears that a planned dose level is associated with an unacceptable frequency of toxicities, then an intermediate dose or alternative administration schedule may be evaluated, and will not initially exceed a dose determined to be tolerable. After preliminary evaluation of safety and PK data from these intermediate dose or alternative administration schedules, re-escalating doses of BMS-986288 may be initiated (see [Table 2-2](#) and [Appendix 8](#)). The study will first evaluate the safety and tolerability of BMS-986288 monotherapy based on dose-limiting toxicities (DLTs), using a Bayesian Logistic Regression Model (BLRM) employing the escalation with overdose control (EWOC) principle [REDACTED], and overall assessment of available safety, PK, and pharmacodynamic data.
- The Safety Evaluation of BMS-986288 in Combination with Nivolumab (Part 1B) will evaluate the safety and tolerability of various doses of BMS-986288 in combination with nivolumab to determine the combination MTD/RP2D. Treatment in Part 1B will be initiated in a staggered manner relative to the BMS-986288 Monotherapy Escalation (Part 1A). Specifically, Part 1B can be initiated upon the decision to escalate when at least 2 dose levels in Part 1A have cleared the DLT period in accordance with dose escalation rules, after which dose escalation in Part 1A and Part 1B will proceed in parallel (see [Section 7.2](#)). At no point will the dose of BMS-986288 administered in combination with nivolumab in Part 1B exceed the highest safe dose in ongoing monotherapy dose escalation in Part 1A or the highest dose determined to be tolerated in Part 1A. In Part 1B, the dose of BMS-986288 will be escalated, whereas the dose of nivolumab will be [REDACTED] mg [REDACTED]. However, if it appears that a planned dose level is associated with an unacceptable frequency of toxicities then an intermediate dose level, additional cohorts of alternative BMS-986288 administration schedules, or de-escalating doses of nivolumab may be evaluated, and potential re-escalating doses of BMS-986288 may then be initiated (see Table 2-2 and Appendix 8). The safety and tolerability of the BMS-986288 combination with nivolumab will be evaluated using a BLRM-copula employing the EWOC principle, and an overall assessment of available safety, PK, and pharmacodynamic data.

- The [REDACTED] of BMS-986288 as a Monotherapy and/or in Combination with Nivolumab [REDACTED] may be conducted to obtain preliminary data on the safety, tolerability, PK, bioavailability, and pharmacodynamics of BMS-986288 alone or in combination with nivolumab when [REDACTED] will be initially composed of a single cohort for BMS-986288 monotherapy (Arm A) and/or BMS-986288 in combination with nivolumab (Arm B). The dose and administration schedule of BMS-986288 alone or in combination with nivolumab selected for [REDACTED] will be determined by evaluation of the available safety, PK, and pharmacodynamic data from Part 1A and Part 1B, [REDACTED]. BMS-986288 may be combined with [REDACTED] depending on the dose selected (Arm A and/or Arm B). Nivolumab in combination with [REDACTED] may also be administered (Arm B). The BMS-986288 dose in [REDACTED] will not exceed the highest dose equivalent determined to be tolerated in Part 1A and/or Part 1B. [REDACTED] may be used to inform [REDACTED] dose selection in The Initial Expansion Phase (Part 2).

Part 2: The Expansion Phase is where cohorts of BMS-986288 [REDACTED] (Part 2A) and Combination with Nivolumab (Part 2B) are expanded to gather additional safety, tolerability, preliminary efficacy, PK, and pharmacodynamic information in specific participant populations.

[figure not shown]
- One or more dose regimens of BMS-986288 alone and in combination with nivolumab selected for Part 2 cohort expansion will be selected from the range of doses assessed as tolerable in Part 1, and which do not exceed the MTD or highest dose administered. These dose(s) will be selected based on evaluating the recommendation from BLRM and an overall assessment of available safety, PK, pharmacodynamic, and efficacy data from Part 1.
- Part 2 is currently comprised of signal-seeking expansion cohorts in cutaneous melanoma, NSCLC, and a randomized MSS CRC cohort in comparison with regorafenib; additional tumors or potential arms will be included upon evaluation of available safety, PK, pharmacodynamic, and efficacy data from Part 1.

All participants will complete up to 3 study periods: Screening (up to 30 days), Treatment (up to [REDACTED] cycles, [REDACTED] days/cycle), and Follow-up (comprised of Safety [100 days], Imaging [up to 2 years], and Survival [up to 2 years] following end of treatment [EOT]). The duration of study participation will be approximately 4 years (treatment of up to 2 years and follow-up of up to 2 years).

Images will be submitted to a central imaging vendor and may undergo blinded independent central review (BICR) at any time during the study. Prior to scanning first participant, sites should be qualified and understand the image acquisition guidelines and submission process as outlined in the CA043001 Imaging Manual provided by the central imaging vendor.

The study design schematic is presented in [Figure 5.1-1](#). A detailed schematic for study period and participant flow is presented in [Figure 5.1-2](#).

**Figure 5.1-1: Study Design Schematic**

Abbreviations: 3L/4L = 3rd/4th line; BMS = Bristol-Myers Squibb; CRC = colorectal cancer; CTLA-4 = cytotoxic T-lymphocyte-associated protein 4; IRT = Interactive Response Technology; [REDACTED] MSS = microsatellite stable; NSCLC = non-small cell lung cancer; PK = pharmacokinetics; [REDACTED]  
[REDACTED] RCC = renal cell carcinoma; [REDACTED] RP2D = recommended Phase 2 dose; [REDACTED] [REDACTED] SCCHN =  
squamous cell carcinoma of the head and neck; TBD = to be determined; TNBC = triple-negative breast cancer.

a Prior anti-PD-(L)1 therapy allowed. Anti-CTLA-4 naive required.

b Additional doses and dose schedules may be explored using data obtained from [REDACTED] administration.

c Part 1B will not start until demonstration of acceptable safety in at least 2 cohorts from Part 1A. Subsequently, treatment in both parts will occur in parallel.

d Doses(s) will be identified upon clinical evaluation of available safety, PK, pharmacodynamics, and efficacy data in Part 1A and/or Part 1B. [REDACTED] [REDACTED] may be used in combination with BMS-986288 or nivolumab, depending on the determined dose. Details will be provided through a protocol amendment.

[figure not shown]
e Part 2 will be initiated upon evaluation of available safety, PK, pharmacodynamics, and efficacy data from Part 1 and may include [REDACTED] administration.

f Alternative assignment: In Part 2A [REDACTED] and Part 2B Combination Expansion, Part 2A and Part 2B may be open concurrently. In this case, treatment assignments will alternate between Part 2A and Part 2B. Multiple doses may be open concurrently in each part. In that case, treatment assignments will alternate

between the dose levels, with consecutively treated participants assigned to different parts through IRT whenever possible. If there are no openings available in the dose level to which the participant would be assigned by this algorithm, then the participant will be assigned to the next open dose.

g Intermediate dose level ([Section 5.1.2.1](#)).

**Figure 5.1-2:** Study Design Schematic for Expansion Part 2C

[figure not shown]

Abbreviations: 3L/4L = 3rd/4th line; BICR = blinded independent central review; CRC = colorectal cancer; IRT, Interactive Response Technology; MSS = microsatellite stable; [REDACTED].

a Efficacy analyses based on the treated population may be performed for interim analyses (see further details in [Section 10](#)).

b Stratification by liver metastasis status and a cap of 50% participants with liver metastases in each arm. Once enrolled in IRT, participants who have met all eligibility criteria for Part 2C will be randomized in a 2:1 ratio to nivolumab in combination with BMS-986288 (Arm C) or regorafenib (Arm D) and stratified by liver metastasis status. An additional dose of BMS-986288 ( [REDACTED] mg or [REDACTED] mg) in combination with nivolumab may be opened as Arm E.

[REDACTED] (see further details in [Section 5.4.8](#)).

**Figure 5.1-3: Study Period and Participant Flow**

### 5.1.1 Screening Period

The screening period will be up to 30 days and begins by establishing the participant's initial eligibility and signing of the informed consent form (ICF). The screening assessments are shown in [Table 2-1](#). If a participant exceeds the 30-day screening period due to a study-related procedure (eg, scheduling of a [REDACTED] or waiting for a study-related laboratory value), the participant must be re-consented, but does not require a new participant identification number. In this situation, the fewest number of procedures from the initial screening should be repeated to qualify the participant, while maintaining participant safety and eligibility. Within a given disease type, participants meeting all eligibility criteria will be enrolled in the study using an Interactive Response Technology (IRT) according to the part and treatment arm availability.

### 5.1.2 Treatment Period

The initial dosing regimen of BMS-986288 is [REDACTED]. Continuous safety evaluation and tumor assessment occurring in Part 1 and Part 2 ([REDACTED] until Week 48 of treatment and then [REDACTED] thereafter), will guide the decision to treat a participant with additional cycles of study therapy if the participant has confirmed clinical benefit (up to a maximum of 2 years).

Weekly study visits will be performed for the first 8 weeks after the first dose of study treatment for the BMS-986288 Monotherapy Escalation (Part 1A), the Safety Evaluation of BMS-986288 in Combination with Nivolumab (Part 1B), the [REDACTED] of BMS-986288 as a Monotherapy and in Combination with Nivolumab [REDACTED], and the Initial Expansion Phase (Part 2), followed by study visits [REDACTED] thereafter. During the treatment period for all study parts, additional study visits to collect samples for intensive PK, ADA, and cytokine assessments will be required at Cycles 1-6, and every fourth cycle after Cycle 6 until EOT. See [Section 9.5](#) for further details.

For the BMS-986288 Monotherapy Escalation (Part 1A) and the Expansion Phase BMS-986288 [REDACTED] (Part 2A), BMS-986288 will be infused over approximately [REDACTED]. Shorter infusion times may be used for the initial dose cohorts and longer infusion times (approximately [REDACTED]) may be used for the higher dose levels.

For the Safety Evaluation of BMS-986288 in Combination with Nivolumab (Part 1B) and the Expansion Phase BMS-986288 in Combination with Nivolumab (Part 2B and Part 2C Arm C, Arm

E, and Arm Z), BMS-986288 and nivolumab will each be infused over approximately 30 minutes. When both BMS-986288 and nivolumab are given in combination, nivolumab will be given first, over 30 minutes, followed by BMS-986288 over [REDACTED], beginning at least 30 minutes after completion of the infusion of nivolumab. Shorter infusion times for BMS-986288 may be used for the initial dose cohorts and longer infusion times (approximately [REDACTED]) may be used for the higher dose levels.

For the Part 2C BMS-986288 in combination with nivolumab portion of the study, participants will receive the [REDACTED] with the selected BMS-986288 dose [REDACTED] is not possible upon confirmation with the Sponsor. [REDACTED]

[REDACTED], the infusion will be the same as described below). The starting dose will be [REDACTED] mg of BMS-986288. A possible additional arm with a to-be-determined dose of BMS-986288 may be added based on an evaluation of the entirety of the safety, PK, PD, and anti-tumor activity data from Part 1B. When both BMS-986288 and nivolumab are given [REDACTED], the infusion will be given approximately over [REDACTED]. For participants weighing < 40 kg, the total infusion volume will be limited to 80 mL. For the Part 2C Arm D, the participants will receive regorafenib at [REDACTED] mg orally once daily for 21 days of each [REDACTED]-day cycle until disease progression, toxicity, withdrawal of consent, or death, whichever occurs first (see [Section 5.5.4.9](#) for details).

Depending on the dose(s) selected for the [REDACTED] of BMS-986288 as a Monotherapy and/or in Combination with Nivolumab [REDACTED], BMS-986288 and nivolumab may each be [REDACTED] with the [REDACTED] of study treatment should be administered in the abdomen or alternatively in the thigh. Different [REDACTED] sites should be used if both BMS-986288 [REDACTED] and nivolumab [REDACTED] are being administered (Arm B), with nivolumab being given first, followed by BMS-986288. [REDACTED] should not occur into or around an infected or acutely inflamed area because of the danger of spreading a localized infection. Clinical judgement should be used in determining the best site for [REDACTED] drug administration.

See [Table 2-2](#) for the on-treatment Schedule of Activities and [Table 7.1-1](#) for a list of dose selection and timing. Refer to the Pharmacy Manual for additional dose preparation details for BMS-986288, nivolumab, and [REDACTED] (if applicable).

### Sentinel Participant

During the Dose-Escalation Phase (Part 1), a staggered dosing (sentinel participant) approach will be used. The first participant to be dosed at Cycle 1 Day 1 of each dose level will be observed for 5 days, before additional participants (ie, Participant 2 onward in that cohort) receive study treatments in the same dose level.

Initially, 3 participants will be enrolled at the start of each cohort, in accordance with the sentinel participant approach cited above. However, to allow for any unforeseen discontinuations (such as disease progression) before the 5-week DLT period (35 days) is completed, an extra participant may be enrolled in each dose-escalation cohort. Therefore, there may be a total of 4 participants (3 + 1) at the start of each cohort, provided that the fourth participant is able to start dosing within

approximately 1 week of the third participant in the same dose-escalation cohort. Additional information on DLTs can be found in Section 5.1.2.1 and [Section 7.4.1](#).

### **5.1.2.1 Dose-Escalation Decisions for the BMS-986288 Monotherapy Escalation (Part 1A) and the Safety Evaluation of BMS-986288 in Combination with Nivolumab (Part 1B)**

The Dose-Escalation Phase (Part 1) of the study will evaluate the safety and tolerability of BMS-986288, given alone or in combination with nivolumab, based on DLTs, using a BLRM for both Part 1A and Part 1B. The DLT period will be 5 weeks.

During the monotherapy (Part 1A) and combination therapy (Part 1B) dose-escalation phases, a set of approximately 3 participants will be treated at each specified dose level. If the potential DLT occurring in the third evaluable participant regarding the specific dose level does not influence the dose escalation decision by BLRM, the next dose level may proceed without waiting for the third participant to complete the corresponding DLT observation period. In this situation, cohort tolerability assessment and subsequent dose recommendation may occur when at least [REDACTED] evaluable participants within a cohort have completed a 5-week DLT period, after discussion and agreement between the Sponsor and Investigators. Any toxicities that occur beyond the DLT period will be accounted for in making dose level decisions and/or dose level modifications. Additional information on DLTs can be found in [Section 7.4.1](#).

Continuous reassessment of dose recommendation, by BLRM in the BMS-986288 Monotherapy Dose Escalation (Part 1A) and in the Safety Evaluation of BMS-986288 in Combination with Nivolumab (Part 1B), will be carried out for each dose level. The planned dose regimens are shown in the study design schematic in [Figure 5.1-1](#).

Prior to declaring the MTD, and in consultation with investigators, the Sponsor has the option to expand any dose level previously established to be tolerable (during the DLT evaluation) in order to obtain additional experience or to investigate dose levels intermediate to those defined in the protocol (hereon referred to as “backfill”). The Sponsor may choose to enroll only participants with certain cancer types and certain criteria, from dose escalation during backfill, based on emerging data. Planned dose levels may be modified (eg, alternative administration schedule, [Appendix 8](#)), or intermediate dose levels added, based upon the BLRM analysis and clinical evaluation of available safety, PK, and pharmacodynamic data in Part 1A and Part 1B. Dose escalation in the alternative schedule may be performed; cohort tolerability assessment and subsequent dose recommendation will follow the same principles as outlined for the planned administration schedule of [REDACTED].

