## **10 STATISTICAL CONSIDERATIONS**

### **10.1 Sample Size Determination**

#### **10.1.1 *Monotherapy Dose Escalation (Part 1A)***

Dose escalation during BMS-986288 Monotherapy Escalation (Part 1A) will be guided by BLRM employing the EWOC principle █████. The BLRM method is fully adaptive, makes use of all the information available at the time of each dose assignment, not just data from the current dose level, and directly addresses the ethical need to control the probability of overdosing. Furthermore, the BLRM uses the knowledge gained from participants treated with ipilimumab (for Part 1A) or ipilimumab and nivolumab (for Part 1B). The targeted toxicity rate in this study is in the range of (16%, 33%). The boundary is similar to the toxicity boundary used by a rule-based design (ie, 3 + 3 design) in that a minimum is set at 16% (~ 1 in 6) DLT rate and a maximum at 33% (~ 2 in 6) DLT rate. The use of the EWOC principle limits the risk of exposing patients in the next cohort to an intolerable dose by ensuring the posterior probability of the DLT rate at or exceeding 33% at any dose is capped at 35%.

In order to understand operational characteristics of the BLRM, the total maximum number of participants for the simulation will be set to █████. Simulation studies with various scenarios show that the expected number of DLT-evaluable participants needed for BLRM is no more than approximately █████.

For the trial, approximately 4 participants (3+1) will be treated at the starting dose levels of BMS-986288. While the BLRM will use DLT information from the DLT period, clinical assessment will take into consideration of the totality of available data including PK/pharmacodynamic from all treated participants in assigning a dose level for the next cohort. AEs meeting DLT criteria outside of the 5-week DLT period may also be incorporated into the

BLRM and dose de-escalation may be considered as appropriate based on the BLRM recommendation. At least █ DLT-evaluable participants will be treated at the BLRM-recommended MTD (BLRM-MTD). A maximum of █ DLT-evaluable participants will be treated at each dose level. Once the BLRM-MTD is identified, then additional participants may be treated at the BLRM-MTD or any dose level below the BLRM-MTD for further evaluation of safety, PK, or pharmacodynamic parameters as required without exceeding a total of █ evaluable participants.

The BLRM-MTD is the dose that satisfies the following 3 conditions:

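### The early-escalation check tests only the third participant's possible DLT, so in a 3 + 1 cohort it can pass although two pending DLTs together would break the 35% overdose cap

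*Combined protocol and SAP*

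**What the plan says.** Section 5.1.2.1 treats about three participants at each dose level and sets a 5-week DLT period. It then gives an early route, on this condition: "If the potential DLT occurring in the third evaluable participant regarding the specific dose level does not influence the dose escalation decision by BLRM". When the condition is met, escalation need not be held until the third participant's window has closed. The early decision also needs a minimum number of completers, which is redacted: "evaluable participants within a cohort have completed a 5-week DLT period, after discussion and agreement between the Sponsor and Investigators".

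The Sentinel Participant text in Section 5.1.2 allows an extra participant as cover for early discontinuation: "Therefore, there may be a total of 4 participants (3 + 1) at the start of each cohort". The fourth must be able to start within "approximately 1 week of the third participant in the same dose-escalation cohort". Section 10.1.1 plans the same size at the outset: "approximately 4 participants (3+1) will be treated at the starting dose levels".

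Section 10.1.1 also states the overdose safeguard, "ensuring the posterior probability of the DLT rate at or exceeding 33% at any dose is capped at 35" per cent. By Section 7.4.1, a participant counts as DLT-evaluable after stopping for a DLT, or after receiving two doses and completing the window.

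**The concern.** A look-ahead of this kind is sound if no outcome still pending can reverse the decision. In a three-person cohort, testing the third outcome achieves that. In a 3 + 1 cohort the fourth participant starts at about the same time as the third or up to about a week later, so while the third is pending the fourth normally is too. If both stay evaluable, both enter the model. The written check covers 1 DLT in 3 but not 2 DLTs in 4.

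At stake is whether the early route keeps to the overdose control that the design relies on. A new cohort could start at a dose that the completed data of the previous cohort would have barred.

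**Working it through.** **What can be reproduced.** The 35% is a design constraint, not a computed result, and the model's prior and doses are not available. The one Bayesian boundary with open inputs is the Part 2 rule in Section 10.3.8.1: prior Beta(0.5, 0.5), stop if P(rate > 33%) > 0.80. With 40 treated, 16 events give 0.827 and 15 give 0.731, so the stated boundary of 16 out of 40 reproduces.

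**Which pending outcomes matter.** Assume two participants have completed without a DLT. The completer number is redacted; not waiting for the third suggests two.
- Tested by the rule: third has a DLT, 1/3.
- One DLT among the third and fourth: 1/4, which is less adverse than 1/3 and so already covered.
- Both have a DLT: 2/4, which is not tested.

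**Illustrative model (all inputs assumed).** logit p(d) = log α + β log(d/d_ref), with independent normal priors on log α (centred at logit 0.10, a median DLT rate of 10% at d_ref) and on log β (centred at 0). Doses double. Earlier cohorts are 0/3 each. The table gives P(DLT rate ≥ 33%) at the next dose, to be compared with 0.35.

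| Setting | 1/3 | 1/4 | 2/4 |
|---|---|---|---|
| A: SD 1.0 (log α), 0.5 (log β); four lower doses; d_ref = current dose | 0.32 | 0.28 | 0.53 |
| B: SD 1.5, 0.7; three lower doses; d_ref = next dose | 0.22 | 0.19 | 0.45 |

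In both settings the written check passes and 2/4 exceeds the cap.

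**Sensitivity.** In setting A, moving d_ref down one level gives 0.51 at 1/3, so the check itself blocks. Moving it up one level gives 0.24 at 2/4, so the cap holds. Either move removes the gap.

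A wider grid of 480 assumed settings used prior median 11–33%, SD of log α 1–2, SD of log β 0.7–1, dose steps of 1.5, 2 or 3 times, and several reference and current-dose positions. The written check passed in 262. In 151 of these (151/262 = 58%) 2/4 broke the cap, and in 111 it did not. This is a count over assumptions, not a probability for this trial.

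**How likely two pending DLTs are.** The matching quantity is the predictive probability E[p(current)² | 0/2 at the current dose, 0/3 at each lower dose]. It is 1.2% in setting A and 0.5% in setting B.

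**The case against.** The case against giving this much weight is strong in several respects.

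- **The cap is not breached when the decision is taken.** Section 10.1.1 applies the model to the information available at each dose assignment. A reader might infer that the rule lets the trial escalate in violation of overdose control. The documents do not support that. The issue is only that outcomes still pending could change the answer.
- **The event is rare.** A reader might square a high true rate (0.33² = 10.9%, 0.50² = 25%) and take that as the risk. Such rates sit badly with the history that lets the check pass: no DLT at the current dose or any lower one. Under the same models the figure is about 0.5 to 1.2%.
- **The size rests on unknown inputs.** Moving the reference dose by one level can remove the gap.
- **There are other protections.** The fourth participant is optional, and one who only replaces a dropout creates no gap. Early decisions need Sponsor and Investigator agreement. The model is reassessed continuously, later toxicities are counted, and each new dose starts with one sentinel observed for 5 days.
- **Remaining use may be limited.** Section 5.5.3 already draws on Parts 1A, 1B and 2B to choose the Part 2C dose. Section 5.1.2.1 still allows intermediate doses and escalation on alternative schedules.

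A reader might also extend the point to backfill participants still in their window. Section 5.1.2.1 limits expansion of an existing level to doses already found tolerable, and no calculation here supports that extension.

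Most of this stands and lowers the weight of the point. It does not close the gap, because none of these protections requires the fourth participant's outcome to be tested before the next dose opens.

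**Conclusion.** The point holds as a minor gap in the text. Sections 5.1.2 (Sentinel Participant), 5.1.2.1 and 10.1.1 do not fit together on how a pending fourth participant counts. The check can pass while two pending DLTs would take the posterior probability at the next dose above 35%.

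The illustrations (0.32 against 0.53, and 0.22 against 0.45, for 1/3 against 2/4) show that this can happen. They assume two completers, doubling doses, a 10% prior median and a reference dose at the current or next level. How often it would happen under the trial's own prior and doses cannot be determined from the documents. In these models two pending DLTs are uncommon, at about 0.5 to 1.2%.

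**What to change.** Reconcile the three sections. State in Section 5.1.2.1 that early escalation is allowed only if the BLRM (Part 1A) or BLRM-copula (Part 1B) decision is unchanged under every joint outcome of all cohort participants who are still in their DLT window and whose data will enter the model. This changes which outcomes the look-ahead tests. It proposes no dose and no DLT rule.

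The cost is one extra model run per early decision and, in affected cohorts, loss of the early start. Escalation would then wait for the third participant's window to close. If the third clears, the worst remaining case is 1/4, which is less adverse than the 1/3 that already passed. Only if the third has a DLT would the fourth's outcome, up to about a week later, still be needed.
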